#### **1.3.6 Reinfection following acute HCV infection**

The risk of reinfection is often cited as a reason for not offering treatment to current and former PWID, but few studies have evaluated the incidence of HCV reinfection following successful treatment in this context. The limited evidence would suggest that the reinfection rate is low. Of 111 subjects treated in the ATACH study, viral recurrence after treatment-induced suppression was observed in 19% (17/88) with 5 cases of reinfection (4.7 cases per 100 py; 95% CI 1.9, 11.2) (72). Ongoing IDU during follow up was reported by 38% of participants with treatment-induced virological suppression, with a higher reinfection rate in this subgroup (7.3 per 100 py [95% CI: 2.3, 22.6]). In the ATACH Recall study, 50 individuals from the original ATACH cohort were reassessed at a median duration of 7.2 years following primary infection with 37 (74%) having received treatment (SVR 24 70%) and 10 (20%) having demonstrated spontaneous clearance (73). Only 4 reinfections were identified (with 3 related to ongoing IDU) for an incidence rate of 1.8 per 100 py (95% CI: 0.7, 4.8). Importantly, significant changes were noted in injecting behaviour; 66% (33/50) had acquired HCV via IDU, but only 30% (15/50) reported ongoing use.

Two systematic reviews have examined the risk of reinfection in PWID after treatment-induced SVR, combining studies of acute and chronic HCV infection. In the first, the pooled estimate of reinfection from 5 prospective studies was 2.4 per 100 py (95% CI: 0.9, 6.1), rising to 6.4 per 100 py (95% CI: 2.5, 16.7) in those reporting ongoing IDU post SVR (74). The second systematic review and meta-analysis revealed similar findings with viral recurrence (late relapse or reinfection) in the “high risk” group (PWID, prisoners) estimated at 2.8 per 100 py (95% CI 2.06, 3.71) (75). Contrary to this, reinfection rates in predominantly young adult PWID who exhibited spontaneous clearance are higher, suggesting that this cohort may be at especial risk, though the number of subjects available for assessment was small (76-79).

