## **3 Participant population**

### **3.1 Number of Participants and Participant Selection**

A total of 250 participants with recent HCV infection will be enrolled from drug and alcohol clinics, tertiary liver and infectious diseases clinics and community health centres across Australia, Canada, Germany, New Zealand, Switzerland, The Netherlands, the United Kingdom and the United States. The Kirby Institute may close or suspend screening prior to reaching 250 participants in order to manage the total study enrolment numbers.

The number of participants with HCV/HIV coinfection enrolled to the study will be capped at 70% (or less than 175 participants) of the total study population. In addition, the number of participants with HCV reinfection enrolled to the study will be capped at 50% (or less than 125 participants) of the total study population.

Selection of participants:

Enrolment into the study is at clinician discretion providing participant satisfies all eligibility criteria. However, the following situations should be considered prior to enrolment:

1. It is possible that participants presenting with acute HCV infection may spontaneously clear if followed untreated. Clinicians should consider it unlikely that the patient will spontaneously clear based on viral

load fluctuation before enrolling in this treatment study. It is suggested that a minimum of 4 weeks is observed from presentation to exclude this possibility.

2. Acute participants with very high viral loads (>7 log IU/ml) may be at higher risk of treatment failure. It is suggested to observe these patients until HCV viral load reduces to <7 log IU/ml before enrolling in study.

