### 3.2 Inclusion criteria

Subjects must meet all of the following inclusion criteria to be eligible to participate in this study.

- 1 Participants have voluntarily signed the informed consent form.
- 2 18 years of age or older.
- 3 Detectable HCV RNA at screening (>10,000 IU/ml), and in the opinion of the investigator is unlikely to demonstrate spontaneous viral clearance
- 4 HCV genotypes 1-6.
- 5 HBsAg negative
- 6 Negative pregnancy test at screening and baseline (females of childbearing potential only).
- 7 Male subjects and female subjects of childbearing potential who engage in heterosexual intercourse must agree to use protocol specified method(s) of contraception
- 8 Medically stable on the basis of physical examination, medical history and vital signs
- 9 Adequate literacy to provide reliable responses to the study questionnaires
- 10 All fertile males and females must be using effective contraception during treatment and during the 30 days after treatment end.
- 11 Recently acquired HCV infection (estimated duration of infection ≤12 months)\*

Recently acquired HCV infection as defined by:

A)

i) First anti-HCV Ab or HCV RNA positive within the previous 6 months

and

ii) Documented anti-HCV Ab negative within the 12 months prior to anti-HCV antibody positive result

OR

B)

i) First anti-HCV Ab or HCV RNA positive within the previous 6 months

and

ii) Acute clinical hepatitis (jaundice or ALT > 10 X ULN) within the previous 6 months prior to first positive HCV antibody or HCV RNA, with no other cause of acute hepatitis identifiable

OR

C) For cases of recent HCV reinfection the following criteria are required:

- i) Documented prior HCV antibody positive with HCV RNA negative on at least 2 occasions 6 months apart  
*and*
- ii) new HCV RNA positive within the previous 6 months

\*Estimated duration of infection based on midpoint between last antibody negative or HCV RNA and first antibody positive or HCV RNA in the case of seroconversion and 6 weeks prior to date of maximum ALT in the case of acute hepatitis.

See [Section 3.4](#) for 'Definitions used to calculate Estimated Date of Infection'.

If co-infection with HIV is documented, the subject must meet the following criteria:

1. Antiretroviral (ARV) untreated for >8 weeks preceding screening visit with CD4 T cell count >500 cells/mm^3  
OR

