#### Baseline visit (Week 0)

- Vital signs and physical examination
- HCV RNA (Local laboratory)
- LFTs, FBC and biochemistry
- Pregnancy test (females of child bearing potential only)
- Adverse Events
- Concomitant medication
- Abbreviated Behavioural questionnaire
- Long-Acting Hepatitis C Therapy Questionnaire\*
- Research specimen collection (EDTA plasma, whole blood & ACD Plasma/PBMCs)

\* The Long-Acting Hepatitis C Therapy Questionnaire aims to obtain participant interest and attitudes towards long-acting parenteral hepatitis C therapy. All currently enrolled participants will complete the Long-Acting Hepatitis C Therapy Questionnaire at their next scheduled visit.

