- To evaluate the immunological factors associated with treatment induced clearance and reinfection;
- To evaluate patient interest and attitudes towards long acting parenteral hepatitis C therapy (Long-Acting Hepatitis C Therapy Questionnaire).

Hypothesis

Six weeks treatment with sofosbuvir/velpatasvir is non-inferior to twelve weeks treatment with sofosbuvir/velpastavir as assessed by sustained virological response at 12 weeks post treatment in the intention-to-treat population (SVR12).

Study design (Figure 1)

This is an open label multicentre study. The study consists of a screening phase, treatment phase and follow-up phase to evaluate treatment response and reinfection. Participants will be required to wait a minimum of four weeks from screening before commencing treatment to assess for spontaneous clearance. The maximum wait period allowed between screening and baseline is 12 weeks.

[figure not shown]

Figure 1: Study Schema

Sample size and power

The primary objective of this trial is to establish the non-inferiority of short duration treatment (6 weeks) to the standard duration treatment (12 weeks). Assuming an expected SVR of 90% in the control arm, 113 participants per arm will be required to give 80% chance that the two-sided confidence interval of the difference between regimens has a lower limit greater than -12%.

A total of 250 subjects enrolled and randomised will comprise the intention-to-treat (ITT) population and will form the study population for evaluation of the primary and secondary endpoints.

TYPE OF ANALYSIS

This document describes the primary statistical analysis for REACT study in accordance with protocol version 5.0.

Data Safety and Monitoring Board (DSMB) Analysis

This study has a DSMB to review the progress and safety of the study. The DSMB conducted an interim safety and adherence analysis when the first 50 participants had either reached post-treatment week 12 or dropped out of the study and then when a further 10 per arm reached 12 weeks post treatment. At the second review the DSMB recommended termination of the short arm of the study due to inferiority. At the stage of the DSMB recommendation, a total of 196 participants had been randomised, 192 had completed their randomised treatment, a further 4 were randomised to receive 6 weeks and extended to 12 weeks. Therefore, the primary analysis population will be based on 192 participants (99 in standard Arm, and 93 in shortened arm).

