Primary analysis: Post-treatment week 12

The analysis for the primary endpoint, SVR12, will be conducted after all participants have completed the post-treatment week 12 visit or prematurely discontinued from study. All the safety and efficacy data through to the post-treatment week 12 visit will be cleaned, finalised, and included for the analysis.

GENERAL CONSIDERATIONS FOR DATA ANALYSES

Statistical Methods

Analysis results will be presented using descriptive statistics. For categorical variables, the number (n) and percentage of participants in each category will be presented. For continuous variables, the number of participants (n), mean and standard deviation (SD), median, interquartile range (IQR, Q1-Q3), range (minimum, maximum) will be reported; for inclusion in the manuscript, an appropriate determination will be made depending on the variable, size and distribution of the population studied.

Statistical tests will be 2-sided and performed at the 5% significance level unless specified.

For all efficacy endpoints, means and proportions with two-sided 95% confidence intervals (CI) will be determined. For the analysis of categorical outcomes, Chi-squared tests or exact equivalents (for small numbers) will be used. For comparison of continuous measures, t tests or non-parametric equivalents will be used as appropriate for the observed data distribution. Changes in injecting behaviour between screening, end of treatment and post-treatment week 12 will be compared using the McNemar test (exact binomial probability).

Analysis Sets

Analysis sets define the subjects to be included in an analysis. The number of participants eligible for each analysis set will be provided. Participants who were excluded from each analysis set will be summarised, with reasons for exclusion.

Full Analysis Set (ITT population)

The FAS includes all enrolled participants who were randomised. This will be the analysis set used for the primary efficacy and safety endpoints. Following the DSMB recommendation to cease the study, the primary analysis population will be based on 192 participants (99 in standard Arm, and 93 in shortened arm).

Modified Full Analysis Set

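### The wait before treatment is meant to assess spontaneous clearance, but no entry, randomisation or analysis rule uses the baseline HCV RNA, so participants who have cleared can be counted as SVR12 successes

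*SAP*

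**What the plan says.** **Purpose of the wait.** The SAP, under Study design, states: "Participants will be required to wait a minimum of four weeks from screening before commencing treatment to assess for spontaneous clearance". It adds: "The maximum wait period allowed between screening and baseline is 12 weeks".

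**Entry.** Protocol 3.2, item 3, requires: "Detectable HCV RNA at screening (>10,000 IU/ml), and in the opinion of the investigator is unlikely to demonstrate spontaneous viral clearance". No other criterion sets a current HCV RNA level, and none refers to the baseline value. Protocol 3.1 adds guidance: "Clinicians should consider it unlikely that the patient will spontaneously clear based on viral" load fluctuation before enrolment, and "It is suggested that a minimum of 4 weeks is observed from presentation to exclude this possibility".

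**Baseline.** HCV RNA is drawn at week 0 (Protocol 6.1, Baseline visit), and the Synopsis has eligible participants start treatment at that visit. Section 6.1 requires a quantitative HCV RNA result only at screening.

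**Randomisation.** It takes place between weeks 5 and 6 of treatment (Protocol 4.2 and 6.1). The baseline HCV RNA is not mentioned there, nor in the discontinuation criteria of section 4.3.

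**Analysis.** The SAP states: "The FAS includes all enrolled participants who were randomised". The mITT set removes non-virological failures and reinfections. The per-protocol set depends on doses received and on having virological follow-up to SVR12. SVR12 needs only HCV RNA below the LLOQ 12 weeks after treatment stops. Baseline HCV RNA appears in SAP Table 7 as a mean or median and as a candidate factor for outcome.

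**The concern.** The wait has a stated purpose, and a sample that could serve it is taken at the end of the wait. No rule then acts on the result. The criterion in section 3.2 is a forecast made by the investigator. It does not tell a site or an analyst what follows when the day-0 result is below the LLOQ.

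Someone who has cleared before the first dose is expected to be HCV RNA negative 12 weeks after treatment whatever the assigned duration, unless reinfected. Such participants add successes to both arms and carry no information on 6 against 12 weeks. Both SVR12 rates rise, and the difference moves towards zero. If 6 weeks is truly worse, that is the anti-conservative direction for a non-inferiority comparison. None of the three efficacy sets (FAS, mITT, PP) would show it.

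**Working it through.** **Inputs from the documents**
- Control SVR12 90%, margin −12 points, 113 per arm, 80% power (Protocol 11.1; SAP, Sample size and power).
- Two-sided 5% level (SAP, Statistical Methods).
- Primary analysis population: 99 standard, 93 shortened (SAP, DSMB Analysis).

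**The plan's own figure.** With equal arms at 90%, the unpooled formula gives n = 0.18 × (1.960 + 0.842)² / 0.12² = 98.1, so 99 per arm. A restricted-maximum-likelihood (Farrington–Manning) variance gives 110.2, so 111. A continuity correction gives 114.2, so 115. The stated 113 lies between the last two; the documents do not name the method. The point below does not depend on it.

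**Dilution model.** Let c be the fraction already cleared at day 0. It is equal across arms on average, because randomisation comes later. Suppose all of them reach SVR12. Then

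- observed arm rate = c + (1 − c) × rate in viraemic participants
- observed difference = (1 − c) × true difference

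Take the true rates at the margin, 90% and 78%. For c = 5%: 0.05 + 0.95 × 0.90 = 90.5% and 0.05 + 0.95 × 0.78 = 79.1%, a difference of −11.4 points.

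**Chance of falsely declaring non-inferiority.** This is the probability, from exact enumeration of both binomials, that the lower limit of a 95% Wald interval exceeds −12 points. The Wald form is an assumption, since the documents do not name the interval.

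| c (assumed) | Standard / short rate | Difference, points | 113 per arm | 99 / 93 |
|---|---|---|---|---|
| 0 | 90.0% / 78.0% | −12.0 | 2.8% | 2.9% |
| 1% | 90.1% / 78.2% | −11.9 | 2.9% | 3.1% |
| 2% | 90.2% / 78.4% | −11.8 | 3.1% | 3.2% |
| 5% | 90.5% / 79.1% | −11.4 | 3.7% | 3.8% |
| 10% | 91.0% / 80.2% | −10.8 | 5.0% | 5.0% |

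A normal approximation gives slightly lower values: 2.5% at c = 0, 3.3% at 5% and 4.3–4.5% at 10%.

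**Scale in people.** Of 192 participants, c = 1% is 0.01 × 192 ≈ 2, c = 2% is about 4, c = 5% about 10 and c = 10% about 19.

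**What is known about c.** The documents give no clearance rate for a 4–12 week wait after the screening filter. The nearest figure, in Protocol 1.3.6, is "10 (20%) having demonstrated spontaneous clearance" among 50 members of an earlier cohort, reassessed at a median of 7.2 years after primary infection. It is not a rate for this wait, and the relevant fraction should be smaller.

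**No true difference.** If the arms are equal, (1 − c) × 0 = 0. The difference is then unbiased, although both SVR12 rates are still raised.

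**The case against.** **Guards exist.** Section 3.2 makes the investigator's opinion mandatory, and section 3.1 points to viral load fluctuation, which implies more than one measurement. A reader might infer that cleared participants are in fact being randomised. The documents do not show that; they show only that nothing objective prevents it. This stands and limits the claim.

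**One low value is not clearance.** Section 3.1 itself speaks of fluctuation. For reinfection cases, section 3.2 asks for two negative HCV RNA results 6 months apart. A single day-0 result below the LLOQ may therefore come from someone still infected. This stands and limits what any exclusion can prove.

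**Not every cleared participant succeeds.** The SAP counts death and loss to follow-up as failure, and a reinfected participant is not a success under ITT. The factor 1 − c is therefore an approximation.

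**The short arm was stopped.** The SAP records that the DSMB recommended ending the short arm for inferiority. A reader might infer that the trial is heading for a false non-inferiority claim; that history makes it unlikely.

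**Stronger remedies.** It is tempting to make the viraemic subset the primary population, or to require a quantifiable baseline result before randomisation. ITT is written into the hypothesis, and replacing it in an open-label trial after a stop for inferiority would invite criticism as post hoc. A gate at weeks 5–6 would affect people already on drug. The result might also not be on file: the local baseline test need not be quantitative, and central samples are shipped in bulk (Protocol 10.1).

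**Already visible.** Table 7 summarises baseline HCV RNA by arm. Values below the LLOQ of 10 IU/mL are set to 9, so a reported minimum could reveal one case but not how many.

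**Conclusion.** The gap holds: the plan states why participants wait, measures HCV RNA at the end of the wait, and has no rule that uses the result. Participants who have cleared can enter the primary analysis as successes, which raises both SVR12 rates and shrinks a true deficit by the factor 1 − c.

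The size rests on c, which is assumed, and on true rates of 90% and 78%. At 1–2% the effect is small: 0.1–0.2 points. At 5–10% it is 0.6–1.2 points, with false non-inferiority at 3.7–5.0%. There is no bias in the difference if the arms do not differ. With the short arm stopped, the remaining risk is mainly an understated difference and overstated SVR12 in each arm. This is a cheap improvement to the SAP and does not show that the primary analysis is invalid.

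**What to change.** Keep ITT as the primary analysis. In the SAP:

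1. Report by arm the number of randomised participants whose day-0 HCV RNA on the central EDTA sample is below the LLOQ, and the number with no day-0 result. Name the day-0 sample explicitly: the SAP's general rule takes the last value on or before the first dose date, so a screening value could stand in for a missing one.
2. Prespecify one sensitivity analysis of the SVR12 difference, with its 95% interval, in randomised participants with quantifiable day-0 HCV RNA. The sample precedes dosing and randomisation, so excluding on it does not break the randomised comparison.

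If the count is zero in both arms and no day-0 result is missing, one line settles the matter.

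The stated purpose of the wait in the SAP should also be reconciled with Protocol 3.1, 3.2 and the baseline visit in 6.1, so that the documents say what the baseline result is for. How such participants are managed is a clinical matter, outside this point.

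Cost: one extra analysis and a few lines of SAP text, with no new visit or sample, since EDTA plasma is already collected at baseline and the SAP already plans central testing at all scheduled visits. Slightly fewer participants enter the sensitivity analysis, and some of those left out may have had a fluctuating viral load and not cleared.

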## **12 Data Safety and Monitoring Board (DSMB)**

A data safety and monitoring board (DSMB) will consist of at least 1 statistician and 2 practicing gastroenterologist/infectious diseases specialists. All DSMB members will be independent of the study and the Kirby Institute. The meeting will include the interim efficacy and safety analysis which will be performed when the first 50 subjects in each arm have either received treatment and completed 12 weeks of follow-up post treatment (SVR12) or dropped out of the study. Additional DSMB meetings will be scheduled at a frequency commensurate with the risk as determined by the DSMB.

The Principal Investigator and the institution where the study will be conducted will permit study-related monitoring, audits, ethics committee review and regulatory inspection providing direct access to source documents.

Data will be collected on study specific electronic or paper copy case record forms. The Principal Investigator is responsible for ensuring the data collected are complete, accurate and recorded in a timely manner.

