	To evaluate patient interest and attitudes towards long acting parenteral hepatitis C therapy (Long-Acting Hepatitis C Therapy Questionnaire)	Not included in primary analysis	

Primary efficacy endpoint

The proportion of participants with HCV RNA below the level of quantitation (target not detected [TND] or target detected, not quantifiable [TDnq]) at 12 weeks post end of treatment (SVR12)

The primary analysis will compare randomised treatment groups on an ITT basis including all available data. The primary endpoint, SVR12, will be calculated for each patient based on all available data. Treatment arms will be regarded as non-inferior if the difference in proportion between regimens has a lower limit greater than -12%. Secondary analyses will compare randomised treatment groups based on available data (per protocol).

Secondary efficacy endpoints

- Virological endpoints
 - The proportion of treated participants with:
 - ETR (defined as undetectable plasma HCV RNA at the end of treatment)
 - SVR4 (defined as undetectable plasma HCV RNA at post-treatment week 4)

For virological endpoints, the point estimates and 95% exact confidence intervals will be reported by study arm, by HCV genotype and by HIV serostatus.

Virological endpoints (Table 13 and 14)

The presence of HCV RNA will be assessed at all scheduled clinic study visits using Aptima HCV Quant Dx assay, version 2.15.5 (lower limit of quantitation [LLOQ] 10IU/mL; Hologic, Inc., Marlborough, MA, USA), with centralised testing performed at St Vincent's Centre for Applied Medical Research (Sydney, NSW, Australia).

Proportions and 95% confidence intervals will be reported for both the primary and secondary virological endpoints. Virological endpoints will be assessed in the ITT, mITT and PP populations, with results stratified by HCV genotype/subtype and HIV serostatus.

Factors associated with treatment outcome in the ITT population will be evaluated by univariate analysis. Variables assessed will include but are not limited to: demographic factors (age, gender); virological factors (baseline HCV RNA, genotype 1 subtype, duration of HCV infection); risk behaviors (injecting drug use, sexual behavior, mode of HCV acquisition); HIV co-infection; treatment factors (adherence).

Primary safety endpoints

The primary safety endpoints are:

- Proportion of participants with common adverse events (reported by greater than 5% of the study population);

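### Does the undefined word 'inferiority' in the account of the early stop leave the primary conclusion open?

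*SAP*

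**What the plan says.** **Interim reviews.** Protocol section 12 plans an "interim efficacy and safety analysis which will be performed when the first 50 subjects in each arm" have reached SVR12 or dropped out. It allows further meetings at the board's discretion and gives no stopping boundary. The SAP (Data Safety and Monitoring Board (DSMB) Analysis) reports what was done: "The DSMB conducted an interim safety and adherence analysis when the first 50 participants" had reached that point, and "then when a further 10 per arm reached 12 weeks post treatment".

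**The stop.** The same SAP paragraph says that "At the second review the DSMB recommended termination of the short arm of the study due to inferiority". Under Full Analysis Set the SAP has: "Following the DSMB recommendation to cease the study, the primary analysis population will be based on 192 participants". Both paragraphs give 99 in the standard arm and 93 in the shortened arm.

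**The final analysis.** The SAP (Primary efficacy endpoint), like protocol section 11.3, has one decision rule: "Treatment arms will be regarded as non-inferior if the difference in proportion between regimens has a lower limit greater than -12" percent. Under Statistical Methods it sets two-sided 95% confidence intervals for efficacy endpoints and adds: "Statistical tests will be 2-sided and performed at the 5% significance level unless specified". It also says: "For the analysis of categorical outcomes, Chi-squared tests or exact equivalents (for small numbers) will be used". Table 13 has columns for the difference with its 95% CI and for a P value. No text says which result would be called inferior.

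**The concern.** A non-inferiority trial can end in three ways: non-inferior, clearly worse, or neither. The plan names only the first. Yet the SAP already records that the short arm was ended for inferiority, with no threshold attached. A reader could fear that an in-between result might be reported as 'non-inferiority not shown', as 'no significant difference' or as 'inferior', whichever suited.

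The accounts of the reviews add to the unease. The protocol says efficacy and safety; the SAP says safety and adherence, which as worded does not explain a stop on efficacy. The protocol counts 50 in each arm; the SAP counts 50 participants. One SAP paragraph says the short arm was to end, another says the study. If the primary conclusion depended on any of this, the trial's headline would not be pre-specified.

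**Working it through.** **1. The plan's own figure.** Protocol section 11.1 and the SAP give 113 per arm: SVR12 90% in the control arm, margin 12 points, 80% power, two-sided interval. Assume a true difference of zero and a 95% interval.

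- Simple formula: n = (1.960 + 0.842)² × 2 × 0.9 × 0.1 / 0.12² = 98.1, so 99.
- With continuity correction: (98.1/4) × (1 + √(1 + 4/(98.1 × 0.12)))² = 114.2, so 115.
- Farrington-Manning score formula: 111.
- Exact power at 113 per arm with a continuity-corrected Wald interval: 0.800.

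The stated 113 is consistent with the rule based on the lower limit and a 95% interval.

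**2. How much the undefined word could vary.** Assume about 90% SVR12 in the standard arm and Newcombe intervals (the SAP names no interval method for the difference). The table shows the smallest observed deficit that meets each possible reading of inferiority.

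| Reading | 60 per arm (54/60 standard) | Final, 93 v 99 (89/99 standard) |
|---|---|---|
| Lower limit at or below -12 | 1.7 points | 2.8 points |
| Upper limit below 0 | 15.0 points | 10.3 points |
| Upper limit below -12 | 28.3 points | 24.3 points |

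The word is loose. The question is whether anything in the final analysis uses it.

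**3. An in-between result.** Take 75/93 = 80.6% (shortened) and 89/99 = 89.9% (standard).

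- Difference: 0.8065 - 0.8990 = -0.0925.
- Wilson limits: 0.7147 to 0.8739 and 0.8240 to 0.9442.
- Newcombe lower limit: -0.0925 - √(0.0918² + 0.0452²) = -0.195.
- Newcombe upper limit: -0.0925 + √(0.0675² + 0.0750²) = 0.008.
- Wald interval: -0.0925 ± 1.96 × 0.0509, or -19.2 to 0.7 points.
- Chi-squared: pooled proportion 164/192 = 0.854, standard error 0.0510, z = -1.82, P = 0.069.

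Set against the plan:

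- *Rule on the lower limit:* -19.5 is below -12, so non-inferiority is not shown. This is the answer to the primary hypothesis.
- *Two-sided 5% test:* equality is not rejected. This does not contradict the first statement.
- *The stop:* what the board recommended earlier. It is history, not an output of the final analysis.

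These three statements can all be true together, so they are not rival headlines.

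**4. How often this zone arises.** Exact binomial enumeration at 93 v 99 with Newcombe intervals, counting trials with lower limit at or below -12 and upper limit at or above 0:

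| True difference | Standard arm 90% | Standard arm 95% |
|---|---|---|
| -5 | 53% | 36% |
| -10 | 45% | 30% |
| -15 | 20% | 9% |
| -20 | 5% | 2% |

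The 95% column is relevant because protocol section 1.2 reports 95% and 96% for 12 weeks in chronic infection. These percentages take no account of the stop. In every such trial the existing rule returns the same primary conclusion.

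**5. What an added inferiority rule would tell the reader.** An upper limit below 0 and a chi-squared P below 0.05 in the same direction disagree in at most about 1% of trials with a 90% standard arm and about 3% with 95% (true differences -5 to -20). Table 13 already prints the interval and the P value, so the rule would add a word and almost no information.

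**6. The interim descriptions.** A second review is within protocol section 12. Both reviews are timed on post-treatment week 12, and the stated reason is inferiority, so SVR12 by arm was very probably seen. A further 10 per arm follows naturally from 50 per arm, which suggests that the SAP's count is shorthand. Ending one arm of a two-arm trial ends the comparison, and both SAP paragraphs arrive at the same 192.

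**The case for a change.** The best case for a change is that the ambiguity is real and cheap to remove. Neither document defines inferiority or cites a charter that does. The SAP text postdates the stop, so the word is on record before the final analysis, and moderate true deficits make an in-between result likely. If an upper limit below 0 were used as an unadjusted claim at 50 per arm, 60 per arm and the end, the chance of a false claim with equal arms would be about 3.9%, against about 2.2% for a single final look. About five sentences would settle the matter.

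Part of this stands. The accounts do differ on content, count and what was stopped, and a trial report will have to reconcile them and give the board's criterion or say that none was set.

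The rest does not carry a change to the plan. No objective or hypothesis seeks a claim of inferiority, so there is no confirmatory error rate to protect for it. Stopping because the short arm looks worse does not inflate false claims of non-inferiority. A rule for the label would now be written with the stop already known, which takes away most of its value as pre-specification. The criterion for the stop may lie in a charter that was not supplied, and it would not set the final conclusion in any case.

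**Conclusion.** The concern is right about the text and wrong about the consequence. Inferiority is undefined, and the interim descriptions are loosely worded. The primary question is still non-inferiority, and the hypothesis, the 95% level and the -12 point limit are all fixed. Followed exactly, the plan gives the same estimate, interval, margin, population (99 and 93) and primary conclusion whatever the word meant to the board.

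The in-between zone covers 5% to 53% of trials at true deficits of 20 down to 5 points with a 90% standard arm, and 2% to 36% with 95%. Those figures rest on the assumed control rates and on Newcombe intervals; the conclusion does not, because the rule gives one answer throughout the zone. Analysts would sensibly report a failure of the rule as non-inferiority not shown, with the P value read as a test of equal SVR12 and the stop described as conduct. What remains is a difference in record-keeping between protocol section 12 and two SAP paragraphs, which the trial report can clear up without altering the analysis.
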